Mental health services in Nigeria are deficient in quantity and quality. It is estimated that there is currently one psychiatrist to one million inhabitants and 40:1,000,000 for psychiatric nurses. [21] Furthermore, distribution of the available professionals is grossly skewed in favour of urban areas. The organization of mental health services is top-heavy; at the apex of the pyramid are 8 federal neuro-psychiatric hospitals and about 20 departments of Psychiatry at University Teaching Hospitals. Referral systems are cumbersome and not patient-friendly. Health workers at the secondary and primary levels including Doctors and Nurses have little practical training in or awareness of mental health issues. This leaves majority of rural dwellers who constitute majority of the population underserved. The notion of universal coverage and the Sustainable Development Goal mantra of 'leaving no one behind' will remain unattainable if these circumstances persist.

Study design

This is a cluster-randomized trial involving ten LGAs with the highest number of notified leprosy or BU cases between 2014 and 2018, purposively selected from 220 LGAs in south-east/south-south Nigeria. Five LGAs namely, Ebonyi, Ogoja, Ogbaru, Ogbia and Calabar South were randomized as intervention LGAs and five comparable LGAs – Etinan, Ethiope East, Obubra, Anambra East and Isoko South will serve as control. For allocation of clusters (LGAs) to intervention and control groups, a computer-generated list of random numbers was used.

Baseline survey will be done in the first year of the project in both intervention and control LGAs to determine the magnitude of depression using Patient Health Questionnaire-9 (PHQ-9); generalized anxiety disorders using Generalized Anxiety Disorders-7 (GAD-7), self-stigma using Stigma Assessment and Reduction of Impact (SARI) scale and quality of life using WHOQOL-BREF and Warwick-Edinburgh Mental Well-being Scale (WEMWBS) among eligible persons affected by leprosy/BU.

Attitude of health workers and community leaders towards leprosy/BU patients will be assessed using Focus Group Discussions (FGDs) and Key Informant Interviews (KII). Additionally, social distance scale (SDS) will also be used for community leaders.

Intervention

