The intervention will be at three different levels expected to work synergistically with the intention to reduce mental disorders and improve quality of life among persons affected by leprosy/BU. Therefore, the intervention will include the following:

• Engaging selected community members as lay counselors for basic mental health management:

Advocacy visit to community gate-keepers will provide a platform to identify suitable and willing community leaders who will be trained to serve as lay counsellors for persons affected by leprosy/BU. Depending on the size of each LGA, at least 5 persons will be selected per LGA so that leprosy/BU patients will not need to travel long distances to access care. Following baseline assessment of their perception by trained research assistants using the social distance scale (SDS) and FGDs, their capacity as lay counsellors for the identification and basic management of depression and general anxiety disorders will be built. The 3-day training will be facilitated by Psychiatrists/Clinical Psychologists, Leprosy/BU programme team and Person affected by NTD. Topics to be covered include: i) basic facts about leprosy and BU; ii) screening for depression and GAD using PHQ-9 and GAD-7; iii) basic skills for counselling and psychosocial support; iv) need for social inclusion for persons affected by NTDs; and v) team work/appropriate referrals. After the training, they will be supportively supervised to provide counselling services to leprosy/BU patients with mental disorders and promote their social participation in communities. Laycounsellors represent a critical link between the formal health system and patient's selfhelp groups. Supervision will be done through phone calls and online meetings reinforced by quarterly visits and yearly re-training by research team/mental health experts.

Formation of self-help groups (SHG) among persons affected by leprosy or BU.
Persons affected by leprosy/BU will be organized into self-help groups. The SHGs will be for all patients whether they have mental health problems or not. At the outset, a baseline

assessment of level of self-stigmatisation among these persons will be carried out by trained research assistants using the SARI Stigma scale.

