Health workers from primary healthcare units will be trained on screening persons affected by leprosy/BU for mental health problems using PHQ-9, GAD-7 for depression/GAD and WEMWBS for quality of life; providing pharmacological and psychosocial treatment and/or effective referrals to psychiatrists/clinical psychologists for severe cases. Topics covered in the training include those of community lay-counsellors in addition to basic treatment for common mental disorders especially depression and GAD and supportive referrals to appropriate levels of care.

• Inter-linkage of services and collaboration among the three pillars of care:

Healthcare workers and community lay-counsellors will hold joint review meetings with SHGs at agreed locations once every two months. During interactive sessions, project progress will be re-appraised and challenges to optimal mental healthcare, social participation and well-being of leprosy/BU patients in the community addressed. In-between meetings, members/leaders of SHGs who observe features suggestive of mental illness in any member will report same to community lay-counsellor who evaluates and provides basic counselling after documentation. Whenever necessary, the community lay-counsellor contacts the healthcare worker on behalf of the patient and supports patient to receive required attention including chemotherapy or referral to psychiatrist/clinical psychologist through the health worker after documentation. New cases of leprosy/BU who report to facilities will also be referred by healthcare workers to the nearest SHG while providing routine services.

The intervention phase will take 1 to 2 years with quarterly community sensitization during supervisory visits by research team to promote social inclusion, raise awareness on mental health problems and availability of services to create demand and enhance utilization. Re-training of service providers and self-help groups will be done twice throughout the project period. All assessments done at baseline will be repeated post-intervention in both intervention and control groups, to capture any changes. If successful, the project will provide evidence for a holistic, community-oriented approach for improving access and utilization of mental health services which can be scaled-up nationwide.

Study population:

The study involves three key populations: community opinion leaders, healthcare workers and self-help groups of persons affected by leprosy/BU.

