Community opinion leaders will serve as lay-counsellors for patients with mental health disorders. These may include religious leaders, school teachers, retired civil servants, youth and women leaders and other respected members of the community. At least five lay-counsellors will be selected per LGA.

The primary healthcare workers include nurses and community health officers(CHOs). They will work with community leaders to provide mental healthcare in form of pharmacotherapy and psychotherapy to diagnosed patients as well as ensure referral to psychiatrist/clinical psychologist whenever necessary. At least five healthcare workers will be recruited per LGA.

Inclusion criteria

- Any person affected by leprosy/BU
- All persons affected by leprosy/BU registered for treatment from 2014 up to one year before end of intervention.
- Participants aged between 15 to 65 years.

Exclusion criteria

- Refusal to give consent
- Patients who need urgent medical attention
- Patients unable to communicate clearly

Sample size calculation

A study in Nigeria revealed that 58% of leprosy patients have mental disorders. [4] This study anticipates that 50% of respondents will have mental disorders and 35% reduction is desired after intervention. A study demonstrated that training of community lay-workers could reduce prevalence of depression by more than 20%. [15] A World Bank study revealed 22% of Nigerians are depressed.[22] Therefore, sample size calculation for matched pairing at power=80%; p=0.05 and anticipated 30% loss to follow up is 400 leprosy patients (200 each group: intervention/control). Calculation was powered by leprosy alone, because data on mental disorders among BU patients are unavailable. However, it is known that many features (disfigurements and

stigma) known to result in mental health disorders are similar in both diseases. All eligible BU patients will be included.

2.5.6 Data collection methods:

Data will be collected from persons affected by leprosy/BU at baseline and post intervention and from community leaders and healthcare workers in intervention and control LGAs. Data collection tools include: PHQ-9, GAD-7, WEMWBS, SARI stigma scale, WHOQOL-BREF, SDS, FGD/KII guides, Log-books kept by community leaders and SHGs and registers for routine leprosy/BU data collection. Data will include:

- Bio-demographic information

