- Prevalence of mental disorders among persons affected by Leprosy/BU using PHQ-9 as screening tool for depression and GAD-7 (see annex for tools) to screen for GAD.
- Attitude of community leaders towards leprosy/BU patients using SDS and FGD/KII.
- Stigma perception among persons affected by leprosy/BU using SARI Stigma scale
- Quality of life and mental well-being of persons affected by leprosy/ BU using WHOQOL-BREF and WEMWBS.
- Perception of healthcare workers on mental well-being of leprosy/BU patients using FGD/KII.

The study and control groups will be compared after intervention to determine change in mental health status, quality of life and social participation of study participants.

Data quality will be guaranteed by:

- Training and supervision of research assistants
- Double transcription of voice recordings of KIIs and FGDs

Validation of study tools

Prior to field work, a short validation will be done to validate the WEMWBS tool in all relevant study sites in Nigeria.

This involves:

- Translation/back-translation of tool in Pidgin English, Igbo and Efik languages
- Conduct interviews to ascertain how well tool is understood (interpretability).
- Several rounds of translation/back-translation with 5-10 persons.

• Further validation will be done during field work.

Recruitment

To recruit study participants, first, names and contact details of leprosy or BU patients will be obtained from LGA Leprosy and Buruli ulcer Treatment Registers, respectively. Eligible persons will be contacted by phone calls through the LGA Tuberculosis and Leprosy Supervisors (LGTBLS) and invited for orientation meeting on a scheduled date. Newly detected, eligible leprosy or BU patients registered for treatment at the health facilities during intervention will also be evaluated for depression and GAD by healthcare workers using the research tools and thereafter introduced to nearby SHGs. All leprosy/BU patients who are eligible regardless of mental health status will be enrolled into SHGs up to one year before end of intervention. However, patients who come after the deadline will join the SHGs and receive appropriate services, but not included in final research analysis. All suspected cases of BU or leprosy found by community leaders or members of SHGs will be referred to health workers for diagnosis.

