For recruitment of community opinion leaders, advocacy visit to community gate-keepers to introduce the project will precede identification of suitable persons in the community. Criteria for selection should include: residence in community, age above 18 years, completion of basic education and willingness to provide psychosocial support to persons affected by leprosy/BU. Selected community members have no prior professional training on mental health and should win the acceptance of persons affected by leprosy/BU. Both healthcare workers in the area and persons affected by leprosy/BU including leaders of their SHGs will be involved in the search or nomination of suitable community opinion leaders who will be trained as lay-counsellors and social advocates for patients in the community. This will be done during advocacy meeting with persons affected by leprosy/BU and healthcare workers. This process will ensure the recruitment of suitable persons for the project.

To recruit study healthcare workers, LGTBLS of each LGA will be requested to provide basic information on primary healthcare facilities and healthcare workers in the LGA during the advocacy visits. The health workers shall be contacted through phone calls and invited to participate in focus group discussions (FGDs) on a scheduled date to ascertain their perception on

mental health services for persons affected by leprosy or BU. At least two FGD sessions will be conducted with PHC healthcare workers purposively selected in each LGA. LGTBLS will serve as key informants for the key informant interviews (KII). During the intervention, at least 5 healthcare workers from different PHC centres in each LGA will be selected for training on provision of mental health services. Priority will be given to health workers already involved in case management of leprosy/BU patients. The LGTBLS and heads of PHCs will be requested to identify willing and committed health workers who will be trained to provide mental health services to leprosy/BU patients. Consideration for recruitment will include those who work in areas close to SHGs and also indicate interest in collaborating with SHGs and community leaders in providing services to patients.

Data management

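### In intervention LGAs the only community leaders described as completing the Social Distance Scale are those selected and then trained as lay counsellors, and no rule makes the control respondents comparable

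*Protocol*

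**What the plan says.** **Purpose.** Section 2.5.6 (Data collection methods) lists, among the data to be collected, "Attitude of community leaders towards leprosy/BU patients using SDS and FGD/KII". Under Study design, after the focus groups and interviews: "Additionally, social distance scale (SDS) will also be used for community leaders". The SDS is the only quantitative instrument for this attitude.

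**Respondents.** Under Intervention, the part on lay counsellors, advocacy visits are used to "identify suitable and willing community leaders who will be trained to serve as lay counsellors for persons affected by leprosy/BU". These leaders are the ones measured at baseline: "Following baseline assessment of their perception by trained research assistants using the social distance scale (SDS) and FGDs, their capacity as lay counsellors". A 3-day training follows, with social inclusion as one of its topics. Study population treats the two groups as one: "Community opinion leaders will serve as lay-counsellors for patients with mental health disorders". It sets a minimum of five per LGA.

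**Selection.** Recruitment lists residence, age above 18, basic education and "willingness to provide psychosocial support to persons affected by leprosy/BU". It adds: "Selected community members have no prior professional training on mental health and should win the acceptance of persons affected by leprosy/BU". Health workers and affected persons, including self-help group leaders, take part in the nomination.

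**Repetition.** At the end of Intervention: "All assessments done at baseline will be repeated post-intervention in both intervention and control groups, to capture any changes". Section 2.5.6 collects data from community leaders in both intervention and control LGAs. Data management compares continuous variables between the groups with Student's t test.

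**The concern.** The measure is labelled as the attitude of community leaders. The people described as completing it in the intervention arm are a subset, chosen partly for a quality close to what a social distance scale measures. By endline they have also been trained, supervised and put to work as deliverers of the intervention.

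Two influences other than a change in community leaders' attitude can therefore move the intervention-arm score: who was chosen, and what the chosen were taught. Control LGAs are not described as having self-help groups or counsellors, so the nomination process as written has no evident counterpart there, and no other rule for picking control respondents is given.

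At stake is what an SDS result could be used to claim. The intervention includes quarterly community sensitisation to promote social inclusion. Its effect on leaders who were not trained would go unmeasured by the SDS, and a missing baseline from such leaders cannot be recovered later. Who is measured is a matter for the protocol; an analysis plan cannot repair it.

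**Working it through.** The protocol gives no sample size or power for the SDS, so there is no stated figure to reproduce. The check has two parts.

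**1. The passages side by side**

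| Question | Intervention LGAs | Control LGAs |
|---|---|---|
| Who completes the SDS? | Leaders selected as lay counsellors (Intervention); no others described | Community leaders (2.5.6), not further specified |
| How are they chosen? | Suitability, willingness, acceptance by affected persons (Intervention, Recruitment) | Not stated |
| State at baseline | Selected, not yet trained | Not stated whether selected |
| State at endline | Trained and supervised deliverers of the intervention | Untrained, as far as described |

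The column for control LGAs is open rather than shown to differ.

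**2. How large a shift selection alone could cause (illustration)**

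Inputs:
- From the protocol: 5 intervention LGAs and at least 5 counsellors per LGA, so 5 × 5 = 25 respondents.
- Assumed: 25 control respondents; attitude normally distributed; control leaders unselected; counsellors drawn from the more favourable fraction p of local leaders; correlation r between the selection criterion and attitude.

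Shift in SD units = r × φ(z)/p, where z cuts off the upper fraction p and φ is the standard normal density.
- Upper half: φ(0)/0.5 = 0.399/0.5 = 0.80. With r = 1 the shift is 0.80; with r = 0.5 it is 0.40.
- Upper three-quarters: 0.318/0.75 = 0.42. With r = 1 the shift is 0.42; with r = 0.5 it is 0.21.

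Rejection rate of a two-sided 5% t test on endline scores, no true effect, 48 degrees of freedom, noncentrality = d × √12.5:

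| Shift d (SD) | Noncentrality | Significant |
|---|---|---|
| 0.21 | 0.74 | 11% |
| 0.40 | 1.41 | 28% |
| 0.80 | 2.83 | 79% |

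Clustering, and any narrowing of the SD by selection, are ignored.

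**What a comparison of change would do.** Suppose the baseline offset is b and stays constant. The intervention change is then (b + e) − b = e, and the offset cancels. The table therefore applies to endline levels, not to change. But e is the effect in people who were selected and trained, so it still contains the counsellor training. Ceiling effects, and regression to the mean where selection caught a passing state, do not cancel either.

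**Precision.** With 5 respondents per LGA, the effective number per arm is 25/(1 + 4 × ICC), and the detectable difference at 80% power is (1.96 + 0.84) × √(2/effective n). This gives 0.79 SD at ICC 0, 0.87 SD at 0.05 and 0.94 SD at 0.10. The larger of the assumed selection shifts is thus as large as the smallest effect that the comparison could reliably detect with no clustering.

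**The case against.** The strongest case on the other side has four parts.

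- **The target population may be the counsellors themselves.** Study population equates community opinion leaders with those who serve as lay counsellors. Measuring them before and after capacity building is a coherent process measure. This stands for the before-after use. It does not cover a comparison with control leaders, who are not counsellors as far as the text shows.
- **Control leaders might be chosen in the same way.** Study population and Recruitment state the number and criteria per LGA without limiting them to the intervention arm. This stands as far as it goes: the text neither states nor excludes it. But the criteria are written for finding people to be trained as counsellors, and nomination involves self-help group leaders, who belong to the intervention.
- **The selection is not on the SDS score.** Most of the listed criteria have nothing to do with attitude, and acceptance by affected persons is their view of the leader, not the leader's view of them. This is fair. Willingness to give support may well correlate with social distance, but the strength is unknown, and no ceiling is demonstrated.
- **The consequence is limited.** Neither the primary objective nor any of the seven secondary objectives concerns leaders' attitude. The comparison sentence in section 2.5.6 names only mental health status, quality of life and social participation. This stands.

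A reader might also infer that a between-arm change in attitude cannot be measured at all, or that the leaders were already trained at the baseline SDS. The documents support neither. The SDS is planned at both waves in both arms, so a difference in change can be computed, and the baseline SDS comes before the training. The difficulty lies in what that difference would mean.

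**Conclusion.** The point holds in a limited form. The protocol does not define who completes the SDS in each arm, and for the intervention arm it describes only selected leaders who go on to be trained. An SDS difference between arms, in level or in change, could not be read as a change in community leaders' attitude.

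The figures of 0.21 to 0.80 SD and 11% to 79% show the possible scale of a selection effect on endline scores. They rest on unselected control leaders, assumed selection fractions and correlations, and 25 respondents per arm; the top figure needs a correlation of 1. They are not estimates of bias in this trial. If control leaders were chosen by the same criteria, the selection part would shrink, but counsellor training would remain.

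A reader might infer that the trial's main conclusions are at risk. They are not: this is a supporting measure, and no listed objective depends on it.

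**What to change.** Amend Study design, Intervention, and Study population with section 2.5.6, so that the two uses of the SDS are separate.

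1. **Between-arm comparison.** At the advocacy visit, list opinion leaders in all ten LGAs by the same procedure, before lay counsellors are chosen. Draw the same number per LGA at random from that list, whether or not those drawn are later selected as counsellors. Give these same people the SDS at both waves and compare change between arms.
2. **Lay counsellors.** Report their SDS separately, as a before-after evaluation of training. Do not use it as the intervention-arm sample against control LGAs, or as evidence on community leaders' attitude in general.

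The sample in step 1 should not be confined to leaders who are not counsellors. If control LGAs select none, that would remove the more favourable leaders from the intervention arm only and reverse the bias. Under the model above with correlation 1, the remaining intervention leaders would average −0.80 SD if the top half were selected, and −0.318/0.75 = −0.42 SD if the top quarter were.

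The cost is a short wording change and about 5 extra SDS forms per intervention LGA, so 5 × 5 = 25 per wave, completed by the existing research assistants. The attitude effect reported will probably be smaller.

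### The stated 80% power comes from a calculation with no allowance for ten clusters, an ill-fitting matched-pairing label and an undefined 35% reduction

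*Protocol*

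**What the plan says.** Protocol, Study design: "This is a cluster-randomized trial involving ten LGAs with the highest number of notified leprosy or BU cases between 2014 and 2018". Five named LGAs "were randomized as intervention LGAs and five comparable LGAs" are listed as controls, and for the allocation "a computer-generated list of random numbers was used". No pairs of LGAs are identified.

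Protocol, Sample size calculation: "This study anticipates that 50% of respondents will have mental disorders and 35% reduction is desired after intervention". From this the section concludes: "sample size calculation for matched pairing at power=80%; p=0.05 and anticipated 30% loss to follow up is 400 leprosy patients", split 200 and 200. The calculation rests on leprosy alone. All eligible BU patients are to be included as well, with no number given. The section states no ICC, design effect, cluster size or number of clusters, and no discordance rate or pair correlation.

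Protocol, Data collection methods and Data management: the two arms are compared after the intervention, with a chi-square test for categorical variables and a Student t test for continuous ones. McNemar and dependent t tests are reserved for comparisons such as one group before and after the intervention.

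**The concern.** The protocol fixes its inputs, a method label, a power and a number, so this is not a detail left to a later analysis plan. The calculation does not describe the trial in the Study design section.

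- **Clustering.** The intervention works through lay counsellors and health workers serving an LGA and through self-help groups averaging 15 people. Outcomes within an LGA are therefore likely to be correlated, and five clusters per arm leave few degrees of freedom.
- **Pairing.** The label fits neither the allocation nor the between-arm test. If it refers to the before/after comparison, the stated power belongs to a contrast that is not randomised.
- **Effect size.** The 35% reduction has three readings, and the required number differs about sixfold between them.

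At stake is how the result is read. The sponsor intends national scale-up if the model succeeds. A non-significant result, set beside a claim of 80% power, would count against the model more heavily than this design may justify.

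**Working it through.** **Inputs from the protocol.** Control prevalence 0.50; power 80%; alpha 0.05 (taken as two-sided, since sidedness is not stated); 30% loss; 200 per group; 5 LGAs per arm. Hence 200/5 = 40 enrolled and 40 × 0.7 = 28 evaluable leprosy patients per LGA, or 140 per arm. **Assumed:** equal cluster sizes and an ICC of 0 to 0.10, because the protocol gives none.

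**1. The stated 200.** Individual-level two-sample formula, with d = p1 − p2 and p̄ the mean of the two prevalences:

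n = [1.96√(2p̄(1−p̄)) + 0.8416√(p1q1 + p2q2)]² / d²

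Continuity-corrected: n′ = (n/4)[1 + √(1 + 4/(nd))]². Divide by 0.7 for loss.

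For 0.50 vs 0.325: n = (1.3645 + 0.5766)²/0.175² = 123.0 and n′ = 134.2.

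| Reading of the 35% reduction | n (n′) per group | After 30% loss |
|---|---|---|
| 50% to 32.5% (relative) | 123.0 (134.2) | 176 (192) |
| 50% to 35% | 169.3 (182.4) | 242 (261) |
| 50% to 15% (35 points) | 26.9 (32.4) | 38 (46) |

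The first reading comes closest, but 192 is not 200. A McNemar calculation for 0.50 vs 0.325 gives 126 pairs at zero correlation (180 after loss) and 90 at correlation 0.3 (128). Other variants land at 195 to 199, but only with corrections, correlations or one-sided tests that the protocol does not state. The method used cannot be recovered from the text.

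**2. Power of the design as randomised.** For 50% vs 32.5%:

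- Design effect DE = 1 + (28 − 1) × ICC
- SE = √[(0.25 + 0.219375) × DE/140]
- Noncentrality = 0.175/SE, noncentral t with 10 − 2 = 8 df, critical value 2.306

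| ICC | DE | SE | Noncentrality | Power |
|---|---|---|---|---|
| 0 | 1.00 | 0.0579 | 3.02 | 75% |
| 0.01 | 1.27 | 0.0653 | 2.68 | 65% |
| 0.02 | 1.54 | 0.0719 | 2.44 | 57% |
| 0.05 | 2.35 | 0.0888 | 1.97 | 41% |
| 0.10 | 3.70 | 0.1114 | 1.57 | 28% |

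For comparison, 140 independent patients per arm would give about 85% by the normal approximation. The number is adequate for an individually randomised trial.

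**3. The other readings, same method.** 50% vs 35%: 62% at ICC 0 and 52% at 0.01. 50% vs 15%: 97% at ICC 0.05 and 86% at 0.10; power falls below 80% only at about 0.13.

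**4. Adding BU patients (50% vs 32.5%).** Larger clusters help until SE reaches its floor, √(0.469375 × ICC/5). Power of 80% needs about 46 evaluable per LGA at ICC 0.01 and 83 at 0.02. With unlimited patients the ceiling is 94% at ICC 0.02, 82% at 0.03 and 61% at 0.05 (SE 0.0685, noncentrality 2.55). It crosses 80% at about 0.032.

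**5. Detectable effect.** With 28 per LGA, 8 df and 50% in controls, 80% power requires an endline prevalence of about 29% at ICC 0.01, 27.5% at 0.02 and 23% at 0.05.

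**The case against.** - **The ICC is the reviewer's, not the protocol's.** True, so the size of the shortfall is conditional. A reader might infer that the trial has even odds or worse of detecting its target. That holds only from about ICC 0.03; at 0.01 and 0.02 power is 65% and 57%. The cluster-level test does, however, fall short of 80% even at ICC 0.
- **BU patients will add numbers.** They will, and at ICC 0.01 to 0.02 they could restore 80%. It would be wrong to say they cannot help. They add no clusters, so the ceiling above roughly 0.03 stands.
- **Matched pairing may mean the same person before and after.** Data management does plan a McNemar test for that, so the label may have a meaning. It still does not describe the comparison of arms.
- **The 35% may be absolute.** Power would then be ample. But that reading needs only 38 to 46 per group, and no design effect in the text leads from there to 200.
- **The 8-df test is not the protocol's test.** Correct. The planned chi-square ignores clustering. At ICC 0.01 to 0.05 it would reject roughly 75% to 82% of the time for 50% vs 32.5%, but with a type I error of about 8% to 20% (2[1 − Φ(1.96/√DE)] gives 8%, 11% and 20% at 0.01, 0.02 and 0.05). That apparent power is bought with false positives and is not power at the 5% level.
- **200 is an arithmetic error.** A reader might infer this too. The text does not support it: the method is unstated, and several variants come within a few patients of 200.

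**Conclusion.** The point holds. The 80% is not supported for the trial described: the calculation takes no account of five clusters per arm, its pairing label fits at most a within-group comparison, and its effect size is undefined. On the reading nearest to 200 (50% to 32.5%), a valid cluster-level analysis of the planned leprosy patients has 75% power at ICC 0, falling to 28% at ICC 0.10. The 50% to 35% reading is worse. Only 50% to 15% keeps 80% power across this ICC range, and nothing connects it to 200.

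This rests on equal clusters, exactly 30% loss, a two-sided 5% test and an assumed ICC. It excludes BU patients, whose number could change the answer at low ICC. It does not show that the trial is bound to fail, or what the sponsor's target prevalence is.

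**What to change.** In Sample size calculation:

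1. State whether the 35% is relative or absolute, and give the target prevalence. The sponsor must supply this; it should not be inferred from the 200.
2. Remove matched pairing from the between-arm calculation, or say that it refers to the before/after comparison.
3. Say that 200 per group is an individual-level number.
4. Replace the 80% claim with the power and detectable effect of the fixed five-plus-five LGA design, using 8 df, over a stated ICC range such as 0.01 to 0.10, with and without the expected number of BU patients.

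The cost is wording and a less favourable stated power. No extra patients or LGAs are requested.
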